# 8.2 COMPARATOR: Psychoeducation plus Treatment as Usual

Following randomisation, all young people will receive a website link to a psychoeducation leaflet from the Royal College of Psychiatrists. The leaflet provides information about depression and signposting to where young people can find extra support. Carers (if involved) will also receive carer information regarding depression in young people, as well as signposting for carers.

Usual practice in CAMHS can vary widely (experience of the trial team and in national reports eg CQC 2018). Treatment as usual may be no intervention whilst on an internal CAMHS pathway waiting list; signposting to alternative sources of support; risk and case management; referral to a psychiatrist for medication review; or referral for psychological therapy, however, these generally have long waiting lists. Currently waiting lists for therapy in CAMHS services vary and can be months.

We will record and monitor what treatment as usual means for each young person recruited into the study. We will devise a pro-forma for RAs to complete using clinical records. This will capture all interventions that were delivered in CAMHS, including BA, and recording of risk issues such as attendance at A&E.

When reviewing clinical records we will particularly look for any aspects of treatment as usual that are similar to BA e.g. rating and structuring activities. Even in sites where BA-type interventions may be included in treatment as usual (such as brief psychosocial support), from experience within the associated teams, it is expected that these interventions are sufficiently different to our BA. For example, they are not standardised or do not include key components such as activity scoring.

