# 9.2 Statistical Analysis

Analyses will be conducted in Stata version 17 (or later) following intention-to-treat principles and will follow a detailed pre-specified statistical analysis plan. Statistical

significance will be assessed at the 5% level unless otherwise stated, and 95% confidence intervals will be provided as appropriate. Analyses and results will be reported according to CONSORT guidelines. The flow of individuals through the trial will be reported in a CONSORT diagram, including the number screened (and reasons for ineligibility) and approached for consent (and reasons for non-consent), the number randomised, adherence to allocated treatment, follow-up data completeness and the number of participants included in the primary analysis. Descriptive summaries of continuous data by trial arm will be given in terms of the mean and standard deviation (or median and inter quartile range as appropriate). Descriptive summaries of categorical data will be given in terms of frequencies and proportions. No formal statistical testing will be conducted at baseline. Information on intervention delivery including number and duration of sessions will be summarised descriptively.

The primary outcome (total MFQ-C score) will be summarised descriptively at each time point and analysed using a mixed-effects linear regression model, including all available time points. The model will include trial arm, time, arm-by-time interaction, baseline MFQ score and other important baseline variables as fixed effects. Random effects will be included to account for the repeated measures within patients and for possible clustering by therapist (nested within treatment arm). The primary analysis will compare the groups at 6-months post-randomisation. Secondary analyses will compare the groups at 12-weeks and 12-months post-randomisation. Different covariance patterns for the repeated measurements will be explored and the most appropriate pattern will be used for the final model. Data will be assumed missing at random. Secondary outcomes will be analysed using similar models as described above (with binary outcomes being analysed using a mixed-effects logistic regression model), adjusting for the same fixed and random effects.

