# 11.1 Cost-Utility & Cost-Effectiveness: trial-based analysis

The cost to train the BAY therapists and the cost of their time to deliver the intervention therapy sessions will be estimated as the intervention cost. This will be added to the cost of health and social care resources used by YP in the intervention arm to generate an overall cost for that treatment group. For the TAU+PE group, their overall cost will be generated from their use of health and social resources only. The primary analysis will take the health and social care perspective and so will only include these costs. A secondary analysis will include the cost of 'lost productivity' for parents/carers during the time they spend with YP at (and travelling to) healthcare contacts. Unit costs will be derived from published sources (e.g. NHS Schedule of Reference Costs; PSSRU Unit Costs of Health and Social Care) using the most up-to-date versions at the time of the analysis.

The measure of health benefit in the primary analysis will be YP's QALYs derived from the CHU-9D at baseline and 6-month follow-up. A secondary analysis will derive YP's QALYs from the EQ-5D-Y at these timepoints. QALYs will be estimated using an area under the curve approach.

The difference in costs between the treatment groups will be calculated using a glm regression model with log link and gamma family to account for the typically skewed nature of cost data. The difference in QALYs between the groups will be estimated using a linear regression model. Both regression models will include key covariates, as specified in the statistical analysis. An incremental cost-effectiveness ratio (ICER) will be calculated by dividing the difference in costs by the difference in QALYs between the treatment groups. This will be reported as a cost per QALY. Non-parametric bootstrapping will be used to produce a cost-effectiveness plane to demonstrate uncertainty in the results. A cost-effectiveness acceptability curve (CEAC) will also be generated to illustrate the probability that either treatment is cost-effective at a range of willingness to pay (WTP) thresholds.

The health utility of parents/carers during the study period will be derived from the EQ-5D-5L and compared between the treatment groups.

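### The adjusted log-link gamma model is fitted to a BA-arm cost that is built as a sum, so the incremental cost can be biased by an amount and in a direction set by the covariates

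*Protocol*

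**What the plan says.** All the elements are in Protocol section 11.1.

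- Intervention cost: "The cost to train the BAY therapists and the cost of their time to deliver the intervention therapy sessions will be estimated as the intervention".
- BA arm: "This will be added to the cost of health and social care resources used by YP in the intervention arm to generate an overall cost".
- Comparator arm: "their overall cost will be generated from their use of health and social resources only".
- Estimation: "The difference in costs between the treatment groups will be calculated using a glm regression model with log link and gamma family", chosen because cost data are usually skewed.
- Adjustment: "Both regression models will include key covariates, as specified in the statistical analysis". Section 9.2 names "baseline MFQ score and other important baseline variables as fixed effects". Baseline cost is not named, and section 11 has no covariate list of its own.

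The resulting cost difference is divided by the QALY difference (from a linear model) to give the ICER. Bootstrapping then supplies the cost-effectiveness plane, and a CEAC is generated. Section 11 refers to a health economics analysis plan (HEAP), which is not at hand.

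**The concern.** With a log link, every effect in the model is a multiplier. The model therefore says that BA adds many pounds for a participant whose covariates predict high cost and few pounds for one whose covariates predict low cost. The BA cost, however, enters as an addition. If care costs follow the log-link model and a similar sum is added for everyone in one arm, the total in that arm no longer follows it.

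In a model with a canonical link, the fitted arm means would still equal the observed arm means, and randomisation would rescue the averaged difference. Gamma with a log link lacks that property once covariates are present. The adjusted difference in pounds can therefore settle on the wrong value, even when it is obtained properly by averaging predictions over all participants. A larger trial settles on the same wrong value, and bootstrapping the same model reproduces it.

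At stake is the numerator of the ICER. Cost-effectiveness is part of the primary objective (3.1.1), and section 11.2 makes the long-term model conditional on the trial-based result.

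**Working it through.** **Inputs.** The documents give the link and family, the additive construction, the presence of covariates and, from 9.1, 223 per arm at 70% retention: 223 × 0.70 ≈ 156 analysed per arm. They give no cost figures, so all pound amounts and covariate strengths below are assumptions. There is no stated figure to reproduce.

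**Equations.** Let μ₀(x) be the mean control cost at covariate value x, and μ₁(x) = μ₀(x) + c(x) the mean BA-arm cost. With fitted mean m, the large-sample gamma/log equations are E[Y/m − 1] = 0 within each arm and E[x(Y/m − 1)] = 0 over both arms.

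**Step 1: no covariates.** The arm-only gamma/log model returns the raw mean difference exactly (243.0 against 243.0 in a check). The log link alone does no harm.

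**Step 2: an example that can be checked by hand.** Assume one binary covariate split 50:50, control mean £2,000, twice the cost when x = 1, and a constant BA cost of £500.
- Control means: 2,000/1.5 = £1,333.3 and £2,666.7, ratio 2.
- BA means: £1,833.3 and £3,166.7, ratio 1.727.
- The equations reduce to a fitted ratio t equal to the geometric mean of the two: t = √(2 × 1.727) = 1.859.
- Arm levels at x = 0: control ½(1,333.3 + 2,666.7/1.859) = 1,384.0; BA ½(1,833.3 + 3,166.7/1.859) = 1,768.5.
- Averaged difference: (1,768.5 − 1,384.0) × ½(1 + 1.859) = 384.5 × 1.429 ≈ £550.

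The true difference is £500, so the overstatement is 9.9%.

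**Step 3: the same example with delivery cost rising with x, mean still £500.**
- As steeply as care cost (£333.3 and £666.7): both arm ratios are 2, t = 2, and the result is £500, with no bias.
- More steeply (£200 and £800): BA means are £1,533.3 and £3,466.7, ratio 2.261, and t = √(2 × 2.261) = 2.126. Arm levels are 1,293.7 and 1,581.8, and the difference is 288.1 × 1.563 ≈ £450, an understatement of 9.9%.

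**Step 4: a continuous covariate score, constant BA cost.** With usual-care mean £1,000-3,000 and BA cost £400-1,000, the large-sample overstatement is:

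| SD of covariate effect on log cost | Overstatement |
|---|---|
| 0.2 | 2.3-3.6% |
| 0.3 | 5.1-8.2% |
| 0.5 | 14.1-24.0% |

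With control mean £2,000, delivery mean £500 and delivery cost rising more steeply than care cost, the bias is −5.6% (care slope 0.3, delivery 0.5) and −13.4% (0.5, 0.8).

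**Step 5: simulation at 156 per arm.** Assume care £1,500, BA cost £700 and a variable number of sessions. The planned model averages about £719, £745 and £832 at SD 0.2, 0.3 and 0.5, and about £664 when delivery cost rises more steeply than care cost. Modelling care cost alone and adding the mean BA cost recovered the true difference in every scenario, including the reversed one and those with care savings, at essentially the same SD as the planned model (for example £207 against £207).

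**Step 6: ICER.** Assume a QALY gain of 0.02 and a true cost difference of £500: 500/0.02 = £25,000 per QALY. With the cost overstated to £516.4 (SD 0.2) or £607.1 (SD 0.5), on a control mean of £2,000, this becomes £25,820 or £30,355.

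**The case against.** A reader might infer that the incremental cost, and with it the ICER, is bound to be overstated, always to BA's disadvantage. The documents do not support that.

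- **Delivery cost is not fixed.** The BA completion form records reasons for giving more or fewer than the planned 8 sessions. Feasibility attendance averaged 6.6 (background section), and 10.3 samples interviewees by engagement of 0, under 4, or 4 and more sessions. Nothing says whether delivery cost follows the covariates, and Step 3 shows that this decides the sign.
- **The covariates are unknown.** Section 9.2 names only baseline MFQ, and entry at a score of 27 or more restricts its range. Site is a randomisation stratum, not a listed cost covariate. The remark that "Usual practice in CAMHS can vary widely" concerns the content of usual care, not its cost. Strong prediction of cost is plausible, since service use is collected at baseline, but it is not stated.
- **At modest covariate strength the bias is small beside sampling error.** At SD 0.2-0.3, 2-8% of £700 is about £14-56, against a sampling SD of about £200.
- **The stated reason for the model is skewness.** The protocol does not claim that care costs are truly multiplicative.
- **The HEAP may add arm-by-covariate interactions or sensitivity analyses.**

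The first three points stand, and they limit what can be said about size and direction. The fourth does not remove the mismatch: skewness bears on the choice of family, whereas the link sets how effects combine. The fifth is only partly an answer, because the protocol itself already fixes the outcome, link and family.

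**Conclusion.** The plan fits a model with a common multiplicative arm effect to a total that is additive in one arm, and randomisation does not repair the adjusted difference in pounds. The incremental cost can therefore be biased, and more data will not cure it.

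- **No bias** if the covariates do not predict cost.
- **Overstatement** if they predict care cost and delivery cost is roughly unrelated to them: about 2-4%, 5-8% and 14-24% at SD 0.2, 0.3 and 0.5.
- **No bias, or understatement,** if delivery cost rises with the covariates as steeply as care cost, or more steeply.

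The ICER is overstated only in the second case, and only if the QALY difference is positive. All percentages rest on the assumed cost ranges. The mechanism does not depend on those ranges. This is worth correcting because the remedy is cheap, not because a large error has been shown.

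**What to change.** In 11.1, and correspondingly in the HEAP:

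1. Fit the gamma GLM with log link to health and social care costs, excluding the BA intervention cost.
2. Take the between-arm difference in pounds from predictions averaged over all participants.
3. Add the mean intervention cost over everyone randomised to BA, including those who attended few or no sessions.
4. Carry out all of this inside each bootstrap sample, so that the plane and CEAC reflect both parts.
5. Keep the total-cost GLM as a sensitivity analysis.

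In the Step 2 example the care-cost model is correct (difference £0), and adding the mean BA cost returns £500.

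The change needs a sentence or two, no new data and slightly more analysis work, with essentially no loss of precision in simulation. Linear regression on total cost with the planned bootstrap also avoids the bias but is somewhat less precise. With a constant BA cost of £700 and covariate SD 0.5, its SD was £234, against £203 for the planned model and £205 for the recommended approach. It is a trade-off, and the approach above is preferable.

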# 11.2 Long-term cost-effectiveness: model-based analysis

If there is evidence that the intervention is cost-effective during the study period, then a decision model will be constructed to explore the costs and health benefits over a longer time period. Due to the remitting and relapsing nature of depression, a Markov model is

appropriate for this population. Two alternative scenarios will be modelled for the long-term benefit of the intervention: continuing what was observed in the trial, and attenuating. Targeted literature searches will be conducted to estimate the probability of relapse and remission of symptoms over time in YP. Costs and QALYs will be derived from data collected as part of the trial. Where published or trial data cannot be used to derive model parameters, they will be identified through consultation with experts (clinical and expert by lived experience). ICERs will be generated to estimate the cost-effectiveness of the intervention versus TAU+PE over time. The time horizon for the model will be determined by the mean age of participants at study entry and the likely age they will leave CAMHS services and enter adult mental health services. A discount rate of 3.5% will be applied to costs and health benefits accrued after 12 months, as per current standard practice in England. One-way and probabilistic sensitivity analyses will be conducted to explore uncertainty in the model structure and parameters.

# 12. STUDY WITHIN A TRIAL (SWAT)

#### 12.1 Recruitment SWAT

The recruitment SWAT for the BAY Trial will embed a QR code vs website link into the PIS that takes potential participants directly to the recruitment animation video. Clinics within the NHS Trusts will be cluster randomised to distribute information packs including a PIS with either the QR code or website link. The aim is to see whether the QR code & watching the animation facilitates recruitment into the trial. A protocol for this SWAT has been developed and provided to each study site.

#### 12.2 Retention SWAT

The York Trials Unit has been successful in securing funding for 'Implement SWATs', a project which provides additional funding to host trials to test the effectiveness of various monetary incentives (funded by UK NIHR, award reference: NIHR302256). The BAY Trial will collaborate with Implement SWATs to deliver a retention SWAT, with additional funding to provide unconditional reward (voucher prior to follow-up completion) vs conditional incentive (voucher after completion) at the 6-month follow-up. A protocol for this SWAT has been developed and provided to each study site.

# 13. PATIENT AND PUBLIC INVOLVEMENT (PPI)

PPI will be embedded throughout the project to add impact and value to the research. The aims of involvement from YP and carers are to: shape the research so that it focuses on issues that are most important to them; build capacity so that those involved gain knowledge and skills; provide support and training; collaborate and participate in

dissemination. A broad range of YP with experience of depression and carers will be recruited to our PPI activities:

- 1. Digital panel for website development (8 YP): co-design workshops with the YP Trial Advisory Panel and an active Greater Manchester Mental Health digital PPI group led by PW. Our expert by experience (NR or EW) will join the co-design workshops. Additional co-design workshops will take place during website development with members of the research team.
- 2. Young Person Trial Advisory Panel (8 YP): co-led by PPI leads, SY, EW and NR, will meet throughout the project; additional oversight will be provided by a senior PPI expert. This panel will actively contribute to all aspects of the research, e.g. ethics approval, website co-design, reviewing the content of BA training, participating in training events, participant information, co-producing trial updates for participants eg newsletter, social media, video blogs; evaluating and disseminating findings.
- 3. Carer Panel: led by the carer lead, TW, and SY. 5 additional carers will be recruited across the sites.
- 4. Qualitative PPI: a YP will co-design the qualitative interview schedules and contribute to qualitative analysis workshops (led by PB).

All approaches to PPI and levels of engagement will be encouraged, to ensure that all members are confident in their role and enjoy their experience. Panel members will be reimbursed according to Involve guidance. Members will be recruited through our local organisations and established contacts.

In the initial stages of the project, the PPI members will be asked to review study documentation before submission to ethics to ensure that the language and accessibility is appropriate for the target audiences. PPI members will also be asked to review the trial processes to ensure they are acceptable and feasible, for example how to minimise burden to participants. Throughout the trial there will be additional opportunities to get involved, for example creating and reviewing content for our social media pages and providing feedback on digital elements of the intervention. There will be a range of opportunities for participating in project dissemination activities including cofacilitating and presenting at the dissemination meeting, video-blogs, publication authorship as peer researcher and presenting at conferences.

#### 14. MONITORING, AUDIT AND INSPECTION

We will follow trial monitoring and site monitoring procedures in accordance with the standard operating procedures of both the study trials unit (York Trials Unit) and the study sponsor (GMMH). The conduct of the trial will be governed by the Trial Steering Committee (TSC) that has an independent chair, three independent senior academics, and two representatives of young people and carers. The TSC will meet at a minimum of twice a year to monitor progress and protocol adherence and to advise the study team. The trial will be monitored by a Data Monitoring and Ethics Committee (DMEC) which has an independent chair and two senior academics. The DMEC will meet a minimum of twice a year to monitor the data and ethical processes.

#### 15. ETHICAL AND REGULATORY CONSIDERATIONS

# 15.1. Health Research Authority (HRA) review

Ethical approval in line with NHS Research Ethics Committee (REC) and HRA guidance will be sought for the completion of this trial. Both the REC and HRA will be notified of, and asked to review, any proposed changes to the procedures and/or documentation made during the trial. As no pharmaceutical compounds or medical devices will be used in the study Clinical Trials Authorisation will not be required.

#### 15.2. Ethical considerations

Several ethical issues have been considered to enable the safe running of this trial. First, young people with depression can be vulnerable and may experience distress or worsening symptoms during their participation. All participants entering the trial will be provided with information outlining who to contact if they (or their carer, if applicable) have any concerns or worsening symptoms during participation. This will include providing individuals with the contact information of their local NHS CAMHS duty clinician service which provides urgent assessments during office hours on weekdays. If a participant feels at risk outside of these hours they will be signposted to the out of hours on-call service provided by their local NHS mental health trust which is available 24 hours a day, 7-days per week. In serious situations young people will be directed to present at their local A&E department or call 999. This will be made clear within the participant information sheets and reiterated during the baseline visit with the researcher.

Throughout the research, any potential adverse events (e.g. distress, misunderstandings, deteriorating mental state) will be monitored closely by the research team. We will encourage all participants to speak to their clinical team if they are unhappy about their participation in the research. We will explicitly state in the study information sheets that participants can withdraw from the project at any time and do not have to give a reason. Withdrawal from the research will not impact upon any therapies they may receive now or in the future.

All data collected from participants during the trial will be confidential and will not contain any information that may lead to the identification of an individual. All participants will be assigned with an ID number which will be used on any questionnaires they complete. All ID numbers will be randomly generated and not be based upon any participant identifiable information. All information will be stored securely and adhere to GDPR regulations and the principles of the Data Protection Act (2018) (as described in section 16.3 for more information about data storage).

Finally, as some participants may prefer their baseline and follow-up assessments to be conducted face-to-face, we will adhere to the individual NHS Trust's lone worker policy in these instances, depending on where the researcher is located. This will be adhered to if visits are conducted in non-public locations (e.g. participant homes). This will include enacting a 'buddy system' whereby any researcher conducting a face-to-face visit will inform colleagues appointment times and expected end time. All researchers will ensure

that they inform a colleague of their arrival at a visit and also at their departure. Non-public locations will be avoided where possible, and the first suggestion for an in-person meeting will be at the CAMHS site.

